1.0 Purpose of the Study

The proposed study is the second phase of a project assessing the feasibility and effectiveness of enhancing the early detection of melanomas among women, who are engaging in health promotion by having mammograms. The initial phase of the project framed risk messages, developed posters and brochures with the input provided by women undergoing screening mammograms, and assessed the feasibility of delivering the program during the mammogram visit at the Lynn Sage Comprehensive Breast Center of Northwestern Medicine/ Prentice Women's Hospital. Now, we seek to evaluate performance of skin self-examination (SSE) by women, who receive information during their mammogram appointment, and follow-up with dermatology for a melanoma screening examination.

In the second phase, a more intensive intervention in which women will not only receive information about SSE, but will also receive a reminder to perform SSE one week after the screening mammogram and information on how to schedule an appointment with dermatology will be provided. The number of women who perform SSE at home and find a concerning mole (lesion), number who see a dermatologist, and number who have a concerning lesion biopsied will be compared in two arms of the study 1) women who receive the intensive intervention 2) women who receive the informational brochure about SSE alone.

Our hypothesis is that women who receive more the intensive educational intervention will be more likely to perform SSE at home and schedule a follow-up dermatologist appointment as compared to those who receive the information brochure alone. This project builds upon [name]'s successful SSE training program for melanoma patients that resulted in patients' accurate evaluations of suspicious lesions relative to dermatologists' skin examinations.⁴

The study aims are as follows:

1. Assess whether SSE education introduced during routine screening mammography encourages women to implement SSE at home, find concerning lesions, and seek follow-up with a dermatologist.
2. Assess the effectiveness of additional reminders to perform SSE and providing information on how to schedule follow-up with a dermatologist on participant performance of SSE with identification of a concerning lesion or scheduling a screening examination with a dermatologist without performing SSE.

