A research assistant will be present at the mammography center to collect consent, telephone numbers, iPhone model information, and email addresses to have women sign onto REDCap to complete a survey. A telephone survey will be administered to each woman enrolled in the study in both groups (N=800) one month after the mammogram asking if she performed a SSE at home and whether a follow-up with dermatology was made. An anonymous REDCap survey may be used in place of the telephone call, depending on participant's preferred method of contact preference. Then, three months after the screening mammogram, an anonymous <2 minute REDCap survey will be sent via email to each woman enrolled in both groups to ascertain the number of women who identified that they were at increased risk for melanoma (history of sunburn, history of indoor tanning >10+sessions, family or personal history of skin cancer), performed a SSE at home, found a concerning lesion, made a follow-up appointment with a dermatologist, and had any concerning lesions biopsied. If participants do not complete the REDCap survey in 2 weeks, they will be called and surveyed via telephone. We anticipate a 20% attrition rate (Fig 3). Participants will be offered a \$10 Amazon gift card in appreciation of completing the one month survey and an additional \$10 for completing of a second REDCap survey three months after the mammogram visit.

Effect of SSE education delivered during the mammography experience.

Fig 3. CONSORT diagram for two arms of study

Effect of SSE education delivered during the mammography experience.

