3.3 Research procedures and activities

Follow-Up

1 week after the mammogram, RA will contact participants in group 1 via their preferred method to remind them to perform SSE and schedule a dermatologist appointment if they find a concerning mole. (see attached telephone script)

1 month after the mammogram, the RA will call participants in group 1 and administer a survey to see if they checked their skin and/or made an appointment with a dermatologist.

Effect of SSE education delivered during the mammography experience.

(see attached telephone script) An anonymous REDCap survey may be used in place of the telephone call, depending on participant's preferred method of contact preference.

The survey questions are as follows:

1. Did you read the brochure?
 Yes No
2. Did you check your skin? (If no, please proceed to question #4)
 Yes No
3. If yes, did you notice any concerning moles?
 Yes No
4. If no, will you consider checking your skin in the future?
 Yes No
5. If you found any concerning moles, did you make an appointment to see a dermatologist?
 Yes No

If no, do you intend to do so in the near future?

6. Did you share the brochure with anyone else?
 Yes No
7. If yes, who did you share it with:
 - a) A relative: son, daughter, father, mother, sister, brother
 - b) A friend : woman, man
 - c) Someone I work with: woman, man

REDCap Survey

3 months after the mammogram, an anonymous REDCap survey will be emailed to each woman enrolled in both groups. If participants do not complete the REDCap survey in 2 weeks, they will be called and surveyed via telephone. The following items with relevance to the research:

1. Do you have a history of sunburn? Yes/No
2. Do you have a history of more than 10 indoor tanning sessions? Yes/No
3. Do you have a personal or family history of melanoma? Yes/No
4. Have you ever performed a skin self-examination prior to your most recent mammogram? Yes/No

Effect of SSE education delivered during the mammography experience.

5. Did you perform a skin self-examination after your most recent mammogram?
Yes/No
If no, then go to item 8.
6. Did you find a concerning mole? Yes/No
7. If you found a concerning mole, did you make an appointment to see a dermatologist? Yes/No
8. If you did not perform a skin self-examination, did you still make a follow-up appointment to see a dermatologist for a skin examination? Yes/No
9. Have you had an appointment with a dermatologist yet? Yes/No

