10. If you found a concerning mole and saw a dermatologist, was the concerning mole biopsied? Yes/No
 - a. If yes, was the biopsy done at Northwestern? Yes/No
 - b. If No, were you told by your dermatologist that the skin biopsy was melanoma? Yes/No
11. If you saw a dermatologist, were any other concerning moles biopsied? Yes/No

EMR review

If a woman responds yes to item 9 indicating that they made an appointment with a dermatologist, then the EMR will be checked to ascertain the findings of the dermatologist. The pathology report of biopsied mole(s) will be reviewed and added to the deidentified database.

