3.4 Measures

The number of women with risk factors for melanoma, who performed SSE after the screening mammogram, who found a concerning mole, who saw dermatology, who had a concerning lesion biopsied in each group will be analyzed by descriptive statistics. The difference in proportions of women who 1) performed SSE 2) saw a dermatologist in the educational intervention group from the intensive intervention group will be compared using a χ^2 test. If the woman responded “yes” to follow-up in dermatology, a chart review of the electronic medical record will be performed to assess whether any lesions were biopsied and pathology of the concerning lesions. The accuracy of the woman’s selection of a concerning lesion will be assessed by examining the correspondence rate between the woman’s assessment during SSE and the dermatologist. The overall correspondence rate will be calculated with a random intercept-only mixed logistic regression model. The statistical analysis will be performed by [name], MPH.

Online data

REDCap survey (see page 8 above)

Approvals required

Effect of SSE education delivered during the mammography experience.

[name] obtained permission for this research to be conducted in the Lynn Sage Comprehensive Breast Center of Northwestern Medicine/Prentice Women's Hospital

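### The survey items on what a woman found, and on its biopsy, say only *mole*, while the aims and the stated survey content concern any *lesion*; appointments made but not yet attended also go unrecorded for some women

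*Combined protocol and SAP*

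**What the plan says.** **Where the plan speaks of lesions.** In section 1.0, Aim 1 asks whether the education "encourages women to implement SSE at home, find concerning lesions, and seek follow-up with a dermatologist". Aim 2 defines its outcome as "participant performance of SSE with identification of a concerning lesion or scheduling a screening examination with a dermatologist without performing SSE". Section 3.1 (Study Design, Phase 2) gives the content of the 3-month survey as, among other things, who "found a concerning lesion, made a follow-up appointment with a dermatologist, and had any concerning lesions biopsied". Section 3.4 (Measures) bases the accuracy measure on the woman's selection of a lesion, and says "a chart review of the electronic medical record will be performed to assess whether any lesions were biopsied".

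**Where the printed items speak of moles.** Eight items do so:
- items 6 and 8 of the survey in section 3.2 (Informed Consent, Participant Surveys, and Educational Intervention);
- items 3 and 5 of the 1-month survey in section 3.3;
- items 6, 7, 10 and 11 of the 3-month REDCap survey in section 3.3, for example "6. Did you find a concerning mole? Yes/No" and "11. If you saw a dermatologist, were any other concerning moles biopsied? Yes/No".

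**Where the plan mixes the terms.** Section 1.0 introduces the comparison with "The number of women who perform SSE at home and find a concerning mole (lesion", with *lesion* in brackets as a gloss on *mole*. Section 3.4 lists women who found a mole and women who had a lesion biopsied in the same sentence. The EMR review paragraph in section 3.3 refers to pathology of biopsied moles.

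**The concern.** The outcome the plan states is wider than the question the woman is asked. If she has found a sore, a patch or a new spot that she would not call a mole, the literal answer to 3-month item 6 is No. Several later items depend on that answer, so the loss can spread from the finding to the appointment and to the biopsy.

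Three things are at stake. Aim 2 depends on whether a self-examiner identified a lesion. The correspondence rate needs the woman's own finding to set against the dermatologist's. Section 14.0 (Data Analysis) names biopsy and diagnoses as primary outcomes alongside SSE performance. A biopsy done outside Northwestern is known only through the survey, so what is not asked there cannot be recovered at analysis.

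**Working it through.** The plan states no figure on this point. The check is a trace of the printed 3-month items for a woman who did SSE, found a worrying non-mole lesion and reads *mole* literally.

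| 3-month item | Condition printed in the item | Her route |
|---|---|---|
| 5, SSE after the mammogram | none | Yes |
| 6, mole found | follows Yes to item 5 | No |
| 7, appointment made | a mole was found | does not apply |
| 8, appointment made | no SSE was done | does not apply |
| 9, appointment already had | none | asked |
| 10, 10a, 10b: biopsy, place, melanoma | a mole was found and a dermatologist seen | does not apply |
| 11, other moles biopsied | a dermatologist was seen | applies after a visit, but says *moles* and has no diagnosis question |

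**Aim 2.** The outcome has two routes: SSE with a lesion identified, or an examination scheduled without SSE. She meets the first. With item 6 at No she is not counted there, and having done SSE she cannot enter by the second. Item 9 does not repair this, because it records a visit and not what she found.

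**Correspondence rate.** With no recorded finding of her own, there is nothing to match to the dermatologist's assessment.

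**Biopsy and diagnosis.** If she attended and was biopsied at Northwestern, Yes to item 9 opens the EMR review and the result can be found there. If the biopsy was elsewhere, item 10b is the only survey question on melanoma, and she does not reach it.

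**Appointments.** An attended visit is captured by item 9. A visit booked but not yet attended gives No to item 9 and is recorded by no other 3-month item. At 1 month the only appointment question, item 5, presupposes moles. This gap comes from the conditions on items 7 and 8 as much as from the word: a woman who did SSE, found nothing and booked a check follows the same route. The EMR paragraph describes Yes to item 9 as showing that an appointment was made, but the item asks whether one has taken place.

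**What is not affected.** The two chi-square comparisons in section 3.4, SSE performed and dermatologist seen, can be taken from items 5 and 9, neither of which mentions a mole.

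**Size.** In one arm, expected recorded findings = respondents × SSE rate × find rate × (1 − s), where s is the share of found lesions that women would not report as a mole. The documents give only 800 women and 20% attrition: 800 × 0.80 / 2 = 320 per arm. The rest is assumption. Purely to illustrate, take SSE rates of 50% and 40% and a find rate of 20%:
- s = 0: 320 × 0.50 × 0.20 = 32.0 and 320 × 0.40 × 0.20 = 25.6, a difference of 6.4/320 = 2.0 points;
- s = 0.10: 28.8 and 23.0, difference 1.8 points;
- s = 0.30: 22.4 and 17.9, difference 1.4 points.

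With s equal in both arms, the ratio between arms does not change. Nothing in the documents supports any particular value of s.

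**The case against.** The strongest reply is that the plan never sets up two constructs. It glosses *mole* as *lesion* in section 1.0, section 3.4 itself lists finding a mole as an outcome, and the EMR paragraph says moles too. In a study of melanoma detection, with eligibility set around a sixth-grade reading level, *mole* is a defensible everyday word. The poster and brochure figures are not shown and the telephone scripts are attachments we do not have, so women may be told elsewhere what to count. How respondents read the word is not documented.

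Much of this stands. It rules out the inference that the survey counts one defined event and the chart another: the terms are loose on both sides. It also means that misreporting is a possibility under a literal reading, not an established result. It does not remove the point, because the gloss is absent from the items the woman answers, and section 3.1 says the survey measures lesions.

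A reader might also infer that such a woman is never asked about an appointment, or that the whole survey is confined to moles. The documents support neither. Item 9 is asked whatever the answer to item 6, and Yes to it triggers the EMR review. Items 8 and 9 do not mention moles.

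**Conclusion.** The point holds in a limited form. The eight items on finding and biopsy are narrower in wording than Aims 1 and 2, the stated content of the 3-month survey and the accuracy measure. Under a literal reading, a self-examiner with a non-mole lesion is miscounted on Aim 2, lost to the correspondence analysis and, if biopsied outside Northwestern, lost for diagnosis. On appointments the gap is one booked but not attended by 3 months, together with the 1-month answer, and it reaches every self-examiner who reports no mole.

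The conclusion assumes that some women take *mole* literally and that the unseen materials do not correct this. The size of the undercount cannot be derived from the documents, and the illustrative figures above should not be quoted as an estimate. The defect does not threaten the trial's validity. It is worth correcting because it touches an aim and two named primary outcomes, and answers not collected cannot be added later.

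**What to change.** 1. Use one inclusive term, for example *mole or other skin spot/lesion*, in all eight items (section 3.2 survey items 6 and 8; 1-month items 3 and 5; 3-month items 6, 7, 10 and 11) and in the telephone script.
2. At 1 month and at 3 months, ask every woman whether she made a dermatology appointment, with no condition on SSE or on a finding. At 3 months this replaces the conditional pair, items 7 and 8. The subgroups they were meant to identify can be rebuilt by crossing the answer with items 5 and 6, including the Aim 2 group who scheduled without SSE. Keep item 9 for attended visits.

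The cost is a rewording of the survey items and script before launch, with no extra visits or participants. There is a small downside: some additional benign non-mole findings will be reported, which may lower the correspondence rate.

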3.1 Inclusion Criteria for Patient

Women 18 years of age and older, who are waiting to have a mammogram

Women agree to complete informed consent and registration forms allowing follow-up reminders and access to their EMR record limited to the visit with a dermatologist or primary care physician regarding a concerning skin lesion and the results of the biopsy of the lesion.

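### The tested outcome of having seen a dermatologist has no time anchor or visit reason, so pre-booked and unrelated visits count as successes and dilute the comparison

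*Combined protocol and SAP*

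**What the plan says.** Section 3.4 (Measures) plans a chi-square comparison: "The difference in proportions of women who 1) performed SSE 2) saw a dermatologist". It gives neither a window nor a purpose for the visit.

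The 3-month REDCap survey in section 3.3 (Research procedures and activities) supplies the data:

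- Item 5 is tied to the mammogram: "Did you perform a skin self-examination after your most recent mammogram". A woman who answers no is sent to item 8.
- Item 7 concerns booking after a finding: "If you found a concerning mole, did you make an appointment to see a dermatologist".
- Item 8 concerns booking without self-examination: "did you still make a follow-up appointment to see a dermatologist for a skin examination".
- Item 9 concerns attendance: "Have you had an appointment with a dermatologist yet".

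The EMR review paragraph that follows says: "If a woman responds yes to item 9 indicating that they made an appointment with a dermatologist, then the EMR will be checked". Its purpose there and in section 3.4 is to obtain findings, biopsies and pathology. Neither place uses it to establish why or when a visit was booked.

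The age and setting criterion in section 3.1 (Inclusion Criteria for Patient) is broad: "Women 18 years of age and older, who are waiting to have a mammogram". The exclusions in section 3.2 concern vision, English and cognition or speech. Current dermatology care is not among them. The 3-month survey asks about personal or family melanoma, so women with such a history can be enrolled.

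**The concern.** The hypothesis in section 1.0 is that the intensive arm will be more likely to self-examine and to schedule dermatology follow-up. A visit supports it only if the study could have prompted that visit. A woman whose annual skin check, or visit for some other skin complaint, was booked before her mammogram can truthfully answer yes to item 9. She then counts as an event in section 3.4, whichever arm she is in.

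Such events carry no information about the reminder or the scheduling card. They raise the rate in both arms, reduce the difference between them and add variance. No printed survey asks about existing dermatology care or an appointment already booked, so survey data could not remove these visits afterwards. At stake is a real effect on dermatology follow-up being missed or understated.

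**Working it through.** **Who reaches item 9**

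| Woman | Route | Reason recorded before item 9? |
|---|---|---|
| Self-examined, found a mole | items 5, 6, 7, then 9 | Yes, but for making an appointment |
| Self-examined, found nothing | items 5, 6, then 9 (items 7 and 8 do not apply) | No |
| Did not self-examine | items 5, 8, then 9 | Yes, but for making an appointment |

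No skip removes anyone from item 9. No rule says that a yes counts only if item 7 or 8 was also yes. Where items 7 and 8 apply, they do not separate an appointment made after the mammogram from one made before it.

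**Inputs**

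- From section 3.1 (Study Design): 400 women per arm (800 in all) and 20% expected attrition, so 400 × (1 - 0.20) = 320 evaluable per arm.
- Not in the documents: significance level, power, effect size and visit rates. The 800 therefore cannot be reproduced from a sample-size calculation.
- Assumed: two-sided 5%; study-prompted visit rates a = 11% (intensive) and 5% (brochure only); background rate b the same in both arms and independent of a.

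**Dilution**

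Observed rate = 1 - (1 - a)(1 - b) = b + (1 - b)a. With equal b in both arms, observed difference = (1 - b) × true difference.

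Power = Φ[(d - 1.96·se0)/se1], where d is the observed difference, se0 = √[2p̄(1 - p̄)/320], p̄ is the mean of the two rates, and se1 = √{[p1(1 - p1) + p2(1 - p2)]/320}.

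Worked case, b = 10%:

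- Rates are 0.10 + 0.90 × 0.11 = 0.199 and 0.10 + 0.90 × 0.05 = 0.145, so d = 0.054 and p̄ = 0.172.
- se0 = 0.02984 and se1 = 0.02976.
- (0.054 - 0.0585)/0.02976 = -0.15, so power = 0.44.

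| b | Observed rates | Difference (points) | Power, 320 per arm |
|---|---|---|---|
| 0 | 11.0% v 5.0% | 6.0 | 80% |
| 10% | 19.9% v 14.5% | 5.4 | 44% |
| 20% | 28.8% v 24.0% | 4.8 | 28% |
| 30% | 37.7% v 33.5% | 4.2 | 20% |

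**Sensitivity to the assumed effect**

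| True rates | b = 0 | b = 10% | b = 20% | b = 30% |
|---|---|---|---|---|
| 20% v 10% | 94.5% | 77% | 58% | 44% |
| 10% v 5% | 67% | 33% | 21% | 15% |

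The starting power depends on the assumed effect. The fall with b appears in each case.

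**The case against.** **Items 7 and 8 give item 9 its meaning.** They come just before it, and the word that closes item 9 can be read as asking whether the appointment just described has taken place. The EMR paragraph reads a yes as meaning an appointment was made. This has force: reason is partly collected, and the items could be cross-tabulated. But no instruction restricts item 9, no rule makes the cross-tabulation, and women who examined themselves and found nothing have no preceding appointment item.

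**Any visit is a defensible pragmatic outcome, and Aim 2 deliberately counts screening examinations scheduled without self-examination.** Both are true. A routine-type skin check is therefore not contamination in itself. The difficulty is limited to visits booked before the mammogram or made for an unrelated reason.

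**Bias.** A reader might infer that the test would falsely favour one arm. If background care were 25% v 20%, with 5% study-prompted visits in both arms, the test would reject about 28% of the time instead of 5%. That needs a systematic difference between the women enrolled in alternating weeks. Chance imbalance between individual women is already covered by the 5% error rate, and nothing in the documents shows a systematic one. Such a difference would in any case be an allocation problem, not one created by item 9.

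**Primary outcomes.** A reader might infer that biopsy and diagnosis, named as primary in section 14.0, are contaminated in the same way. Item 10 is conditional on having found a concerning mole. Only item 11, on other concerning moles biopsied by a dermatologist seen, leaves a route open. The visit itself is not among the primary outcomes in section 14.0.

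**EMR review.** A reader might infer that an unrelated visit opens the chart. Section 3.1 (Inclusion Criteria for Patient) and section 13.2 limit access to visits about a concerning lesion or mole. The broader trigger in the EMR paragraph needs aligning with those limits, but the documents do not authorise review of unrelated visits.

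**Unseen forms.** The registration form and telephone scripts are attached but not available here. A question on existing care may already be in them.

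**Conclusion.** The point holds as a dilution problem. Section 3.4 tests an outcome whose only direct attendance item has neither a start date nor a reason, in a population that can include current dermatology patients. Equal background care reduces the difference by the factor (1-b), with no imbalance needed.

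The size is unknown because no visit rate is given. The 11% v 5% illustration starts at almost exactly 80% power by choice of rates, so it shows the direction and steepness of the loss and does not predict it. It also assumes independence of background and study-prompted visits, 320 completers per arm and a two-sided 5% test.

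The documents do not support a claim that the comparison is biased or that the primary outcomes are generally compromised. The change is worth making because it is cheap and because existing care is hard to establish cleanly after enrolment.

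**What to change.** 1. **Reword item 9** in two parts: *Since your mammogram visit on [date], have you seen a dermatologist for a skin check or a concerning mole? If yes, was that appointment made after the mammogram visit?* This keeps the screening examinations that Aim 2 counts.
2. **Add one enrolment question** on whether she already sees a dermatologist or has an appointment booked, unless the attached registration form already asks it.
3. **Define the outcome in section 3.4** as a visit since the mammogram, for a skin check or concerning mole, at an appointment made after the mammogram. Report all dermatology visits by arm as a supporting result.
4. **Use EMR information only within the access limits** in section 3.1 (Inclusion Criteria for Patient) and section 13.2, and bring the trigger in the EMR review paragraph of section 3.3 into line with them. The reworded item, not the chart, should do the classifying.

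The cost is one reworded item, at most one extra question, and short edits to sections 3.3 and 3.4, with no added visits. The 3-month survey is described as anonymous, so relating the enrolment answer to it requires the study number to be carried through. The existing EMR step already needs that link.

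The downsides are fewer events and some recall error about when an appointment was made. This error could differ by arm, since only Group 1 is reminded to schedule. A pre-booked skin check at which a woman showed a mole she found because of the study would count only in the supporting result.
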